### **Secondary Objective**

The secondary objective is to determine the safety of orally administered Imm 124-E in patients with severe AH being treated with steroids.

### **Exploratory Objectives**

The exploratory objectives are to determine the preliminary efficacy of orally administered Imm 124-E in patients with severe AH being treated with steroids.

### **Primary Endpoint**

The primary endpoint is the safety profile of Imm 124-E in this pilot study.

### **Secondary Endpoints**

The secondary endpoints will include:

- Frequency, severity and relatedness of adverse events
  - Proportion of subjects with nausea and emesis
  - Proportion of subjects with diarrhea
  - Proportion of subjects who develop renal failure, encephalopathy or pulmonary compromise
  - Frequency of sepsis
- Changes in endotoxin levels adjusted for baseline levels at day 7 and 28
- Change in laboratory parameters

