**Key exclusion criteria:**

- Cow milk allergy, severe lactose intolerance and/or known or suspected allergy to any of the ingredients in IMM 124-E
- Other or concomitant cause of liver disease (Viral hepatitis, autoimmune liver disease, metabolic liver disease, vascular liver disease).
- Subjects who are known to be HIV positive.
- Active infection or sepsis (pneumonia by X-ray, positive blood or urine culture) Untreated spontaneous bacterial peritonitis based on > 250 polymorphonuclear (PMN) cells or positive culture. All subjects with enough ascites to be deemed safe for paracentesis, will undergo this procedure (as standard of care) to exclude spontaneous bacterial peritonitis.
- Acute kidney injury with serum creatinine > 1.5 mg/dl at time of randomization
- Evidence of acute pancreatitis (by imaging and lipase > 5 x ULN)
- Subjects who are pregnant or lactating
- Significant systemic or major illness that, in the opinion of the Investigator, would preclude the patient from participating in and completing the study.

- Subjects who are non-cooperative or unwilling to sign consent form.
- Active Gastrointestinal bleeding (e. g. hematemesis, melena)

(See body of protocol for full list of exclusions)

**TEST PRODUCT(S), DOSE AND MODE OF ADMINISTRATION:** The placebo and IMM-124E will both be presented as 1200mg of powder for reconstitution in Plastic Aluminium Foil Poly Laminate Pouches (sachets). The appearance of the active and placebo will be indistinguishable. Each subject will take two sachets each morning and then again in the evening. Consequently, each arm of the study will take the same number of doses per day. Subjects in:

- Group A (IMM-124E 2400mg/day) will receive one sachet of active and one sachet of placebo in the morning and again in the evening.
- Group B (IMM-124-E 4800 mg/day) will receive two sachets of active in the morning and again in the evening.
- Group C (Placebo - High protein milk powder) will receive two sachets of placebo in the morning and again in the evening.

**DURATION OF TREATMENT:** 28 Days

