**ENDPOINTS:**

*Mechanistic Endpoints:*

- The sample size is based on a decrease in plasma endotoxin levels (adjusting for baseline) as measured by analysis of covariance across the study groups. This was

chosen based on the mechanism of action of Imm 124-E. The hypothesis is that both active-drug groups are superior to placebo. In prior studies, we have found the standard deviation of endotoxin levels to be 8-10%

- markers of gut permeability
- intestinal inflammation (calprotectin)
- TNF- $\alpha$  and other immune-inflammatory markers
- microbiome-metagenome

*Efficacy related endpoints:*

- number of subjects meeting Lille failure criteria at day 7
- mortality at 30 days, 90 days and 180 days,
- time to drop in conjugated bilirubin by 50%
- change in MELD and sequential organ failure assessment scores and Discriminant Function
- serum bile acids
- liver function tests

*Safety related endpoints:*

- incidence and severity of gastrointestinal events, including nausea, vomiting and diarrhea
- Proportion of subjects who develop renal failure, encephalopathy or pulmonary compromise
- Frequency of sepsis
- Frequency of any other adverse events

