### **Method of Assigning Subjects to Treatment Groups**

At enrollment and after an ICF is signed, subjects will be identified by their subject ID. Subjects with severe alcoholic hepatitis will be screened for this trial from the inpatient services of the participating centers. Informed consent will be obtained after confirming eligibility. Baseline studies will be performed and subjects will be started on prednisolone/prednisone (40 mg/day) and randomized to the study drug 2400 mg, 4800 mg/day, or placebo. Once enrolled at the Screening visit, each subject will be given a unique identification number which will identify both the site and the individual subject. At the time of randomization, the randomization code will be linked to this identifier and this information will be provided to the clinical center by the data coordinating center. This information will be used by the investigational drug pharmacy to dispense the appropriate study drug/placebo to the individual subject.

Subjects will be randomized sequentially, as they become eligible for randomization. If a subject discontinues participation from the study, their unique identifier code will not be reused, and the subject will not be allowed to re-enter this study.

The appearance and packaging of active and placebo powders for reconstitution are identical. Sachets of study drug will be packed in groups of two sachets into sealed cardboard boxes supplied by Immuron Ltd. Each box will have a code which will be matched to the randomization code at the data coordinating center. Following reconciliation of the randomization code with the box code, the investigational drugs pharmacy will dispense enough medication to last 28 days (56 packs, a total of 112 sachets).

A sealed master list of “box codes i.e. the box set number” vs. randomization code will be securely held by Immuron Ltd., the data coordinating center and also in a sealed envelope by each site pharmacy.

To maintain the double-blind design, drug supplies will be dispensed only by the investigational drug pharmacist, according to a written procedure provided by the Sponsor. The pharmacist will not participate in any other study procedure.

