**Table 2: Schedule of Study Procedures**

Schedule of Study Procedures	Screening	Treatment Phase		Follow-up Phase		
	Day-7 to 0	D0	D7	D30	D90	D180
Informed Consent	X					
Eligibility Criteria/Demographics	X					
Medical and Surgical History/Updated	X		X	X	X	X
Medication Record /Concomitant meds	X		X	X	X	X
Physical Exam/Vital signs	X		X	X	X	X
Anthropometric Measurements/Nutrition	X					X
Urine Pregnancy Test	X		X	X	X	
Adverse Event Assessment			X	X	X	X
Liver biopsy (if performed)	X					
Study Drug Compliance Assessment			X	X		

Assessment of Meld, DF, and Child Pugh Scores	X		X	X	X	X
Assessment of Lille Score			X			
Alcohol Addiction Advice per SOC	X		X	X	X	X
Dispense Study Drug		X				
Alcohol AUDIT and NIAAA Six Question Set	X					X
Time Line Follow Back	X					X
Tobacco/Marijuana Use Questionnaire	X					
CBC, Hepatic panel, INR, Basic metabolic panel	X		X	X	X	X
Serum-WBC-endotoxin, FACS analysis of cell types, cytokines, oxidative stress markers, soluble CD14		X	X	X		
Plasma-Metabolomics		X	X	X		
Stool 16 multi-tag pyrosequencing (microbrome), fecal calprotectin		X	X	X		
Urine-Metagenome		X				

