### **Subject Disposition**

Missing values will be explained in individual data tables. No procedures for replacing missing values by estimates will be implemented.

If there is scientific evidence or explanation for one or more outliers, this will be presented together with a statistical test for outlier identification. In case of outliers, the corresponding statistical analysis will be provided with and without these values.

Any deviation from the original statistical plan will be described and justified in the study report.

**Primary endpoint:** The incidence and severity profile of adverse events will be reported for those receiving Imm-124 versus placebo. It is expected that there will be no signals for increased adverse events with Imm-124. The adverse event rates will be enumerated for each group. Proportions of subjects with specific adverse events will be compared using Fisher Exact test. However, no formal hypothesis testing is planned as there is no basis to expect any changes across groups.

**Principal secondary endpoint:** The principal secondary endpoint will be the decrease in plasma LPS (endotoxin) levels (adjusting for baseline) as measured by analysis of covariance across the study groups. This was chosen based on the mechanism of action of Imm 124-E. The hypothesis is that both active-drug groups are superior to placebo. In prior studies, we have found the standard deviation of LPS levels to be 8-10%.

**Subgroup Analysis:** We will perform subgroup analysis based on gender, race, baseline MELD and SOFA scores, and presence or absence of encephalopathy. Given the overall sample size, we do not anticipate having enough power to do meaningful hypothesis testing. We will also do

a multivariable regression analysis of outcomes with these as covariates to determine if they have an independent impact on outcome, and to identify any interaction terms between these covariates and treatment arm. These are primarily designed for hypothesis generation.

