## **Data Safety Monitoring Board**

An independent Data and Safety Monitoring Board (DSMB) to be established by the NIH and TREAT consortium to assess at intervals the progress of a clinical trial, the safety data, and the critical safety endpoints, and to recommend to the NIH whether to continue, modify, or stop a trial.

**Anticipated Outcomes:** Means for continuous variables at end of study will be analyzed adjusting for baseline values using ANCOVA. Proportions will be compared using chi square or Fisher's Exact test. We expect to show a greater decrease in mean circulating LPS levels in those receiving Steroids+ Imm 124-E compared to steroids + placebo. We further expect to demonstrate that those receiving Imm 124-E will have a reduction in MELD, DF, intestinal permeability, markers of intestinal inflammation, markers of dendritic cell activation, pro-inflammatory T-cell and cytokine profile, cholestasis (serum bile acids) and bilirubin.

**Additional pathophysiologic insights:** Microbiome-metagenomic-immunologic-transcriptomic-histologic data from will lend themselves to analyses using a "systems biology approach" to determine how interactions between these contribute to severe AH and how Imm 124-E can modify this. These will provide novel insights on the role of the metagenome in AH and provide additional targets for therapy in the future.

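### The Day 0/Day 180 rule for the Table 3 immune markers cannot supply the planned end-of-treatment comparisons, and the Day 28 endotoxin endpoint is scheduled only at Day 30

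*Combined protocol and SAP*

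**What the plan says.** **Immune markers.** Exploratory Evaluations introduces Table 3 (cytokines and chemokines, NK cells, cytotoxic T cells, complement activation) as analyses that may be done, on samples from Day 0 and Day 180. Interpretation of Labs follows directly. It treats all of these as continuous variables and plans to compare end-of-treatment levels across arms corrected for baseline, as well as the fall from baseline to end of treatment. Exploratory Endpoints plans the same kind of comparison for cytokines and T-cell phenotypes. Table 2 has one row for this blood work, "Serum-WBC-endotoxin, FACS analysis of cell types, cytokines, oxidative stress markers, soluble CD14", marked at D0, D7 and D30 only.

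**Endotoxin.** The Synopsis states: "The sample size is based on a decrease in plasma endotoxin levels (adjusting for baseline". Subject Disposition states: "The principal secondary endpoint will be the decrease in plasma LPS (endotoxin) levels (adjusting for baseline) as measured by analysis of covariance". It names no day. Secondary Endpoints gives the days: "Changes in endotoxin levels adjusted for baseline levels at day 7 and 28". Table 2 has no Day 28 column and no visit window, and it places D30 under follow-up. The Anticipated Outcomes paragraph says "Means for continuous variables at end of study will be analyzed adjusting for baseline values using ANCOVA" and adds "We expect to show a greater decrease in mean circulating LPS levels".

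**The concern.** For the immune markers, two rules in one protocol give different collection days. A site following Exploratory Evaluations would hold samples from before treatment and from about five months after it. A site following Table 2 would hold samples through the end of treatment. Only the second set supports the planned comparison, and a missed sample cannot be recovered. For C3a and immune complexes there is no second rule to fall back on.

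For endotoxin, sites do know when to draw, because Table 2 is clear. What is open is the meaning of the late value. The endpoint names Day 28 and the schedule names D30. The plan does not say whether the late value is meant to be on treatment or shortly after it. If this is left open, the day is settled at the analysis, for the one endpoint with a stated null hypothesis.

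**Working it through.** **Step 1: length of dosing (the plan's own figure).** Method of Assigning Subjects to Treatment Groups has the pharmacy "dispense enough medication to last 28 days (56 packs, a total of 112 sachets". The Test Product paragraph of the Synopsis says "Each subject will take two sachets each morning and then again in the evening".

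- 56 packs × 2 sachets = 112 sachets.
- 112 sachets ÷ 4 per day = 28 days. The plan's figure reproduces.

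**Step 2: day of the last dose.** The protocol does not say whether the first dose is on Day 0 or Day 1, so both are shown.

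- First dose on the morning of Day 0: last dose on Day 0 + 28 − 1 = Day 27.
- First dose on Day 1, or on the evening of Day 0: last dose on Day 28.

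**Step 3: time from last dose to each sample.**

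| Sample day | Last dose Day 27 | Last dose Day 28 |
|---|---|---|
| Day 28 (Secondary Endpoints) | 1 day | 0 days |
| D30 (Table 2) | 3 days | 2 days |
| Day 180 (Exploratory Evaluations) | 153 days | 152 days |

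This counts D30 from Day 0, as the columns of Table 2 imply. Study Procedures and Flow Chart describes the follow-up days as counted after treatment. Taken literally, that would put the draw at Day 57 to 58 (27 + 30, 28 + 30) and the last visit at Day 207 to 208 (27 + 180, 28 + 180). The same section gives a total of up to 180 days, so the count from Day 0 is the reading that fits.

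**Step 4: immune markers, rule against need.**

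| Marker | Exploratory Evaluations | Table 2 | Planned comparison |
|---|---|---|---|
| Cytokines | Day 0, Day 180 | D0, D7, D30 | End of treatment, baseline-corrected |
| Flow cytometry (NK and cytotoxic T cells) | Day 0, Day 180 | D0, D7, D30 (FACS) | End of treatment, baseline-corrected |
| C3a, circulating immune complexes | Day 0, Day 180 | Not listed | End of treatment, baseline-corrected |

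For the first two rows the rules conflict, and only Table 2 serves the analysis. For the third row the only rule gives no sample within 152 days of the last dose.

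**Step 5: does another passage settle the endotoxin day?** Subject Disposition names none, and neither does Table 4 of the sample-size section. The antibody paragraph under Safety Analysis has a window covering Days 28 to 30, but for antibody samples only. Analysis Population dates MELD, discriminant function and liver function at Days 7 and 30, and its list does not include endotoxin.

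**The case against.** The strongest reply is that Day 28 and D30 are two names for one visit. The antibody window runs from Day 28 to Day 30, and Table 2's only scheduled blood draw that fits it is D30. Analysis Population also uses Day 30 as its late time point. This is a fair reading and probably the intended one. It makes the endotoxin part a missing label and window. It does not remove the mismatch, because no passage extends the antibody window to endotoxin.

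The end-of-study phrase in Anticipated Outcomes might lead a reader to infer a third time point, D180, where no endotoxin is drawn. The documents do not support that. The sentence is a general one on continuous variables. The protocol also uses end of treatment (Exploratory Endpoints) and end of study (Interpretation of Labs) for the same microbiome work, whose last stool draw is D30. The phrase is loose and needs only the common label.

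The 2 to 3 day gap holds only for subjects who complete dosing. Those who stop early, including those removed for Lille failure at Day 7, do not fit it.

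On the immune markers, the reply is that they are optional, carry no formal test, and that Table 2 already covers cytokines and flow cytometry. Table 2 also draws plasma for metabolomics at D0, D7 and D30, so a late plasma specimen may exist. All of this limits the weight. It leaves the Day 0/Day 180 rule unable to serve the comparison planned directly below it, and the protocol does not say that the metabolomics plasma is to be used for C3a.

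**Conclusion.** The point holds in two limited parts.

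- **Immune markers.** The Day 0/Day 180 rule is wrong for its stated purpose. It contradicts Table 2 for cytokines and flow cytometry, and it leaves C3a and circulating immune complexes with no end-of-treatment sample. The assays are exploratory, so no confirmatory conclusion depends on them.
- **Endotoxin.** The late time point is Day 28 in the endpoint and D30 in the schedule. The draw is about 2 to 3 days after the last dose, assuming 28 completed days and D30 counted from Day 0. The Day 7 sample is not affected.

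A reader might go further and infer that the endotoxin endpoint cannot be analysed, or that the trial loses power on it. The documents do not support either. A late sample is scheduled, the protocol gives no figure for how fast any effect fades after dosing, and the sample-size table is not tied to a day. The size of any effect on the estimate is unknown, and none is claimed.

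**What to change.** 1. **Exploratory Evaluations:** change the collection days to Day 0 and the same end-of-treatment draw as Table 2. Keep Day 180 only as an addition, if wanted. List C3a and circulating immune complexes in the Table 2 blood row.
2. **Endotoxin:** name one late sample with a stated window, and use that name in Secondary Endpoints, Table 2 and Subject Disposition. Use the same label in Anticipated Outcomes. Either (a) state that it is the D30 visit, shortly after dosing ends, or (b) if an on-treatment value is intended, move only the research draw to the last days of dosing. Leave the D30 safety, compliance and clinical assessments where they are.
3. **Either way,** record the date of the last dose with the draw, so that the interval is known for every subject, including those who stop early.

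Cost: item 1 is wording plus two assay names on draws that already exist; running those assays is still subject to budget. Option (a) is wording only. Option (b) means one earlier research draw, possibly an extra attendance for subjects already discharged. Item 3 is one date on the case report form. The sample size does not change.

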### **Exploratory Endpoints**

[figure not shown]
The exploratory endpoints will include:

- sCD14 levels (ELISA test to be measured at VCU)
- Intestinal permeability Intestinal inflammation (stool calprotectin by ELISA -to be measured at VCU)
- Proportion meeting Lille criteria for futility (Lille score > 0.45) at day 7
- Mortality at day 7, day 30, day 90 and day 180

- Change in MELD score and discriminant function
- Change in liver function
- Intestinal microbiome-metagenome (end of treatment (EOT) comparison) 
- Activation of systemic inflammation: (EOT across group comparison, baseline-EOT comparison)
  - Markers of oxidative stress (measured at IU)
  - T-cell phenotypes (measured at IU)
  - Cytokines for specific T cell subtype and activation of innate immune system (measured at IU)
- Hepatic transcriptome (real time PCR, gene array Illumina in all cases-EOT across group analyses).RNA will also be available for baseline data and gene array with PCR confirmation of key targets will be performed so that variances at baseline across groups can be accounted for.

## INVESTIGATIONAL PLAN

### Overall Study Design and Plan – Description

**Figure 1: Study Schema**

Subjects with severe AH (MELD score  $\geq 20$  and  $\leq 28$ ) about to receive prednisolone (40 mg/day x 28 days) will be randomized to receive either:

- Group A: 2400 mg/day Imm 124-E as 1200mg bid PO
- Group B: 4800 mg/day Imm 124-E as 2400mg bid PO
- Group C: Identical appearing placebo bid PO

Treatment will be for 28 days (**Fig. 1, above**). Given variable outcomes and response to corticosteroid therapy in patients with severe AH, a Lille model was developed by French investigators to identify subjects early in the course of treatment that are unlikely to benefit from continued treatment and in fact might have worse outcome. The Lille model takes into account patient's age, and at the start of therapy total bilirubin, albumin, creatinine, prothrombin time values and total bilirubin level on day 7 of therapy. It projects a 6-month survival probability of patients with a Lille score above 0.45 to be about 25% contrary to patients with a Lille score below this cutoff (85%). Subjects who meet the Lille criteria for failure of treatment on Day 7 or side effects requiring discontinuation of steroids will be removed from the study. Standard of care nutrition support and alcohol cessation recommendations will be provided to all subjects. Alcohol withdrawal will be managed per standard of care.

## **Selection of Study Population**

The subjects will be screened to determine eligibility criteria. Criteria are to be determined at Screening unless otherwise indicated. Those that meet all of the inclusion and none of the exclusion criteria will be enrolled.

### **Inclusion Criteria**

- Men and women aged 21 and above
- Severe AH with:
  - MELD score  $\geq 20$  and  $\leq 28$
  - About to initiate prednisolone treatment, < 7 days of steroid treatment, or treatment naïve.
- Actively consuming alcohol within 6 weeks of entry into the study
- Willing and able to comply with study requirements
- Voluntary written informed consent

### **Exclusion Criteria**

- Cow milk allergy, severe lactose intolerance and/or known or suspected allergy to any of the ingredients of IMM 124-E
- Concomitant cause of liver disease:
  - Hepatitis B: positive surface antigen
  - Hepatitis C: positive HCV antibody and/or PCR
  - Autoimmune hepatitis: (positive ANA >1:160 titer, ALT > AST, and ALT > 300u/L)
  - Budd Chiari syndrome: Hepatic vein occlusion by Doppler sonography
  - Subjects who are known to have Wilson's disease
- Subjects who are known to be HIV positive

- Active infection and sepsis (pneumonia by X-ray, positive blood or urine culture)
- Untreated spontaneous bacterial peritonitis based on >250 polymorphonuclear (PMN) cells or positive culture
- Acute kidney injury with serum creatinine >1.5 mg/dL at the time of randomization
- Evidence of acute pancreatitis (by imaging and lipase >5 x ULN)
- Active gastrointestinal bleeding (e.g. hematemesis or melena)
- Subjects who are pregnant or lactating
- Significant systemic or major illness, that, in the opinion of the Investigator would preclude the patient from participating in and completing the study
- Patients requiring the use of vasopressors or inotropic support in 12 hours prior to randomization
- Liver biopsy, if carried out for clinical indications, showing findings not compatible with alcoholic hepatitis
- Any patient that has received any investigational drug or device within 30 days of dosing or who is scheduled to receive another investigational drug or device in the course of the study
- Treatment for alcoholic hepatitis within 1 month of study entry with corticosteroids or corticosteroid use >1 week immediately prior to the time of entry into the study.

